### **Type of study**

This study was a prospective interventional study.

### **Study setting**

The study was conducted at orthopedics department at Sohag General Hospital.

### **Study period**

This study was performed in the period between May 2022 and April 2023.

### **Patients**

20 patients with displaced metatarsal head fractures were included.

### **Criteria of patient selection:**

#### **Inclusion criteria:**

- Patients with displaced fracture neck metatarsals 2nd, 3rd, and 4th metatarsals.

#### **Exclusion criteria:**

- Poly-traumatized patient.
- Patient with fracture first and fifth metatarsal bone.
- Fracture shaft metatarsal bone.
- Open fractures of the foot.
- Intraarticular fracture of metatarsals.
- Lisfranc fracture.
- Segmental fracture of the metatarsal

### **Methods:**

#### **All patients were subjected to the followings:**

##### **Metaizeau's technique**

Metaizeau's technique was applied to reduce the displaced metatarsal head distally from the fracture in an easier way and to keep the fracture site closed.

**Figure (1):** Second, third, and fourth metatarsals displaced head fractures.

After preparing the metatarsal fracture site for an open reduction. The procedure was performed by the senior surgeon who was qualified in the technique. The patients were placed in the supine position on a radio-transparent operating table. A Kirschner wire with its distal end is placed showing a small bend into the medullar cavity through the lateral margin of the proximal metaphysis of the affected metatarsal using a 5mm skin incision at that level. It were able to ease the pin in by drilling a hole on the side of the metatarsal bone. The skin incision was made over the interosseus space, to use one incision for the two neighboring metatarsal bones. **Figure (23)**

The diameter of the Kirschner wires to be used should be related to the size of the fractured metatarsal medullar cavity. It drove the Kirschner wire anterograde, with the help of an X-ray image intensifier. The Kirschner wire was driven through the endomedullary cavity from the proximal metaphysis, progressing anterogradely towards the displaced distal epiphysis. Once it reached the fracture site, It tried to thread the metatarsal head with the bent distal end of the Kirschner wire.

Subsequently, It rotated the wire 180 to direct its end to the dorsum of the foot so as to provoke a translation effect on the metatarsal head in order to obtain the head reduction, and maintained this reduction with the Kirschner wire. Open reduction was unnecessary all fractures, leaving the fracture site untouched, and preserving the soft tissues, which will collaborate in the healing process of the fracture.

**Figure (2):** Postoperative radiograph showing intramedullary fixation with Metaizeau's technique

#### **Postoperative treatment**

Postoperatively, no weight bearing in a splint during the first 2 weeks was allowed. progressive weight bearing cast for the next 2 weeks was permitted after clinical signs consolidation, pain and tenderness subsidence, and after 4 weeks we removed the cast and set the patient walking without cast but with crutches if needed, and the Kirschner wires were removed 6 weeks following the operation. **Figure (3)**

**Figure (4):** Radiographic consolidation of the metatarsal displaced head fractures after 8 weeks, showing a correct alignment, no angular deviations, and no shortening of the metatarsal bones.

#### **Postoperative follow up**

Outpatient follow-up was conducted immediately post-operative until achieving the union. It was done 4, 8, 24 weeks and 12 months post-operatively. **Figure (5)**

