#### **Postoperative evaluation**

- **Clinically:** neurological and vascular assessment, deformity and stiffness evaluation were done.
- **Radiological:** x-ray imaging was performed in the 4th, 8th and 24th postoperative weeks to evaluate the alignment and anteroposterior and oblique views of the foot.

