## **Statistical Analysis**

Statistical analysis was done by SPSS v26 (IBM Inc., Chicago, IL, USA). Quantitative parametric data were presented as mean and standard deviation (SD). Qualitative variables were presented as frequency and percentage (%).

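### Does follow-up end at union or at 12 months, and does the loose wording undermine the later deformity and stiffness figures?

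*Combined protocol and SAP*

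**What the plan says.** The Postoperative follow up section has two consecutive sentences about duration. The first is "Outpatient follow-up was conducted immediately post-operative until achieving the union". The second is "It was done 4, 8, 24 weeks and 12 months post-operatively".

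Other sections bear on how to read them:

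- **Postoperative evaluation, radiological.** X-rays are listed for weeks 4, 8 and 24, described as "postoperative weeks to evaluate the alignment and anteroposterior and oblique views of the foot". No condition on union is attached, and no 12-month film is listed.
- **Postoperative evaluation, clinical.** The entry is "neurological and vascular assessment, deformity and stiffness evaluation were done", with no visit named.
- **Postoperative treatment.** A figure legend reads "Radiographic consolidation of the metatarsal displaced head fractures after 8 weeks". It describes one illustration and is not a result for the cohort.
- **Methods.** The opening line is "All patients were subjected to the followings", placed directly above the surgical technique.
- **Statistical Analysis.** Quantitative data are summarised by mean and SD. For the rest, "Qualitative variables were presented as frequency and percentage". No test, model or time-to-event method is named.
- **Study period.** "This study was performed in the period between May 2022 and April 2023".

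**The concern.** An end of follow-up triggered by an event differs from one set by the calendar. A patient who united at, say, week 8 would leave after that visit under the first sentence but would return at week 24 and month 12 under the second. No section says which rule takes precedence.

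If the first rule had been applied, the patients still attending late would be the slow healers. A deformity or stiffness percentage taken at a late visit would then come from fewer than 20 patients, selected by a characteristic plausibly related to the outcome. It would be less precise and could be biased in either direction. The Statistical Analysis section names no denominator, the clinical assessments have no stated visit, and no number seen per visit is given, so a reader could not detect this from the plan. In an uncontrolled series of 20, the denominator carries much of the information.

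**Working it through.** The plan gives no derived figure on this point, so there is nothing to reproduce. The check is a comparison of sections, followed by two short calculations.

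**1. Can the two sentences hold together?** Yes. The second continues the first, with follow-up as its subject, and supplies the dates. Read as one statement, follow-up monitored the fracture to union and took place at four set times. The alternative, discharge at union, would make the week-24 x-ray conditional. The Postoperative evaluation section lists that x-ray without condition, beside the week-4 and week-8 films. The legend showing consolidation after 8 weeks points the same way, weakly: if healing by then were typical, a routine week-24 film would have little place under discharge at union. The line that opens the Methods adds little, since it introduces the operation and says nothing about attendance. The support for fixed visits therefore reaches week 24. Only the second sentence itself supports month 12.

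**2. What would unassessed patients cost?** Inputs: 20 patients (Patients section), *m* of them unassessed at a visit, *x* events seen. The all-patient percentage lies between x/20 and (x + m)/20, a width of m/20.

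| Unassessed, m | Width m/20 |
|---|---|
| 1 | 5 points |
| 5 | 25 points |
| 10 | 50 points |

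With zero events, the exact two-sided 95% upper limit is 1 − 0.025^(1/n).

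| Assessed, n | Upper limit for 0/n |
|---|---|
| 20 | 16.8% |
| 15 | 21.8% |
| 10 | 30.8% |

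The values of m, the denominators 15 and 10, and the zero count are all illustrations; the document reports no event count and no number seen. The figures hold for any series of 20 with missed visits from any cause. They show how sensitive a small series is and do not measure an effect of the union phrase.

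**3. Does the calendar matter more?** Assume that the study period runs from 1 May 2022 to 30 April 2023 (365 days) and covers both surgery and follow-up. The text does not say that it does.

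- Month 12: the earliest operation, 1 May 2022, plus 12 months is 1 May 2023, after the period closes. No patient reaches the visit.
- Week 24: 30 April 2023 minus 168 days is 13 November 2022. From 1 May to 13 November inclusive is 197 days, and 197/365 = 0.540. With operations spread evenly (a further assumption), 20 × 0.540 = 10.8, or about 11 patients.

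If the period describes enrolment only, all 20 could complete every visit. The range is therefore about 11 to 20 at week 24 and 0 to 20 at month 12. These ranges are the same whether or not union ended follow-up, so the calendar question stands apart from this one.

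**The case for a change.** The strongest case for acting is that the literal conflict is real for anyone who united before 12 months, and that clearing it up is cheap: a records check on 20 patients, one sentence, and a count per visit. The missing denominator, the unnamed visit for the clinical assessments and the lack of any missing-data rule mean that a reader cannot exclude selection by healing. Showing the number assessed, and not treating unseen patients as event-free, is sound practice whichever rule was followed.

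Much of that stands. The sentence is loose, union is not defined, the assessment visit is not named, and support from other sections stops at week 24. The harm, however, requires that patients were discharged at union, and no section says that any were. It also requires that deformity and stiffness be reported as late-visit percentages. That is a reasonable inference, but the Statistical Analysis section does not list them among its qualitative variables, and the evaluation section does not say how they were measured. Under the reading that the x-ray schedule favours, there is no selection by union and the only thing left to adjust is wording.

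**Conclusion.** This is loose wording and missing detail, not a demonstrated contradiction, and no change to the plan follows. An analyst would take the four listed visits as the schedule and show how many patients were assessed at each; no planned summary uses union to end observation.

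The effect on results is nil if the listed visits were kept. If some patients did leave at union, neither the size nor the direction of a bias can be worked out, because the document gives no times to union and no attendance counts. The 5 points per unassessed patient is a general property of a series of 20.

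The conclusion rests on reading the second follow-up sentence as the timetable for the first, which the unconditional week-24 x-ray supports. It does not establish that 12-month visits took place. That depends on whether the study period means enrolment only, which the union wording neither causes nor could resolve.

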#### **Postoperative evaluation**

- **Clinically:** neurological and vascular assessment, deformity and stiffness evaluation were done.
- **Radiological:** x-ray imaging was performed in the 4th, 8th and 24th postoperative weeks to evaluate the alignment and anteroposterior and oblique views of the foot.

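### Reduction acts in the dorsal-plantar direction, but only anteroposterior and oblique projections are named for judging alignment, so that direction is not measured directly

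*Combined protocol and SAP*

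**What the plan says.** Three places in the combined protocol and SAP bear on this.

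- **Metaizeau's technique.** The operator "rotated the wire 180 to direct its end to the dorsum of the foot", and does so "so as to provoke a translation effect on the metatarsal head in order to obtain the head reduction". This is the only reduction manoeuvre described. The wire is advanced "with the help of an X-ray image intensifier"; the projections used during surgery are not stated.
- **Postoperative evaluation.** X-rays at weeks 4, 8 and 24 are taken "to evaluate the alignment and anteroposterior and oblique views of the foot". The sentence is garbled, but it gives alignment as the purpose and lists two views ("anteroposterior and oblique views of the foot"). No lateral view is named here or elsewhere, and no angle, displacement measure, threshold or reader is defined. On the clinical side, "neurological and vascular assessment, deformity and stiffness evaluation were done", with no method or scale.
- **Postoperative treatment, Figure 4 caption.** One case is described as "showing a correct alignment, no angular deviations, and no shortening of the metatarsal bones". The caption names neither the plane nor the view.

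The Statistical Analysis section provides descriptive summaries only.

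**The concern.** The direction in which the technique moves the bone is not the direction the named films show best. An anteroposterior film shows length and side-to-side position, and its beam runs roughly along the dorsal-plantar axis. A head left too far plantar or dorsal, or one that slips back later, changes that film little. The oblique film shows such a shift, but reduced in size.

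At stake is what the alignment result can be taken to mean. There is no comparison group and the analysis is descriptive, so a displacement missed on the film passes straight into the reported percentage with acceptable alignment. The error also runs one way, toward a better-looking result.

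**Working it through.** The plan contains no figure to reproduce. The check sets the texts side by side and then applies projection geometry.

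**Step 1: direction corrected.** Metaizeau's technique points the wire end to the dorsum to translate the head. The direction is stated in the text: dorsal-plantar.

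**Step 2: direction imaged.** Postoperative evaluation names an anteroposterior and an oblique view. Neither is perpendicular to the dorsal-plantar axis.

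**Step 3: visible share.** For a parallel beam, ignoring magnification, a displacement of size *d* at angle θ to the beam appears on the film as *d* × sin θ. The plan gives no beam angles, so these are assumptions:

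| View | θ (assumed) | sin θ | Visible share | Lost |
|---|---|---|---|---|
| Anteroposterior, ideal | 0° | 0 | 0% | 100% |
| Oblique, low | 30° | 0.50 | 50% | 50% |
| Oblique, high | 45° | 0.71 | 71% | 29% |

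**Step 4: illustration.** The documents give no displacement size. Taking 4 mm purely as an example:

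- anteroposterior: 4 × 0 = 0 mm
- oblique: 4 × 0.50 = 2.0 mm to 4 × 0.71 = 2.8 mm

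**Step 5: direction of the error.** Since sin θ cannot exceed 1, the projected displacement is never larger than the true one. Under-reading is possible; over-reading from projection is not.

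**Step 6: angulation.** The Figure 4 caption speaks of angular deviation rather than millimetres. For angulation purely in the dorsal-plantar plane, with the bone's length lying across the beam, the sideways component shrinks by the same factor, so tan(apparent angle) = sin θ × tan(true angle). The conclusion is the same in kind. No angle is given in the documents, so no figure is put on it.

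**Step 7: does anything else in the plan fill the gap?** The clinical deformity check has no scale. Intraoperative imaging guides the wire, has no stated projection, and cannot show displacement that arises later, for example after the wires come out at 6 weeks. Neither is a defined dorsal-plantar measurement.

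**The case against.** Much of the opposing case is fair.

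- **The list may not be exhaustive.** The sentence names two views and does not say that no others were taken. A reader might infer that lateral films were never obtained; the text does not establish that. It shows only that none is named. If some exist, the section should say so, and a correction is needed either way.
- **The oblique film recovers part of the displacement.** On the assumptions above it recovers half or more. In principle, two projections a known angle apart would allow the full displacement to be worked out. The plan records no angle and defines no such measurement, so this possibility is not used. The objection does limit the claim to displacement that is not measured *directly*.
- **The 0% is an ideal case.** A tilted beam would show some displacement.
- **Figure 4 captions a single film.** The film could not be inspected and might include a lateral projection. A reader might take the caption as an unsupported result for the whole series; the documents present it only as an illustration. Its wording needs the view added, no more.
- **Alignment is not the only radiographic finding.** Postoperative follow up continues to union, and the Figure 4 caption mentions consolidation and shortening. The missing lateral view does not defeat these, and length shows on an anteroposterior film.
- **Alignment has no defined measure or threshold at all.** This is true and arguably more basic. It means nobody can show how many relevant displacements would be missed. It does not remove the mismatch between the direction corrected and the direction imaged.

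**Conclusion.** The point holds as a limit on what the alignment finding can support. As written, the plan corrects in the dorsal-plantar direction and names no view that measures that direction directly. The visible share is close to nil on an ideal anteroposterior film and about 50% to 71% on an oblique film at 30 to 45 degrees. Alignment findings would therefore tend to favour the technique in the plane it acts on.

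This rests on the two named views being the ones used to judge alignment, on the assumed obliquity, and on parallel-beam geometry. The 4 mm example is illustrative and carries no weight.

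A reader might go further and conclude that malalignment was in fact missed among the 20 patients, or that the radiographic results as a whole are unreliable. The documents support neither: they report no alignment counts, set no threshold, and follow union and consolidation as well.

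**What to change.** These changes are to wording and reporting.

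1. In Postoperative evaluation, repair the sentence and state that alignment is judged on the anteroposterior and oblique projections, if that is the case.
2. Limit any reported alignment result to the planes those projections show.
3. Make no claim about dorsal-plantar alignment unless lateral films already taken in routine care support it. Where such films exist, measure dorsal-plantar position on them and report it separately, with the number of patients who have such films as its own denominator.
4. In the Figure 4 caption, qualify the statement on angular deviation by the view shown.

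The cost is a narrower alignment conclusion, plus the time to measure any existing lateral films. Item 3 may cover only some of the 20 patients, hence the separate denominator. The fix does not depend on new lateral exposures: the text is in the past tense and the study period ended in April 2023, so adding them is probably no longer possible.

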#### **Ethical considerations:**

The study was approved by the Ethics Committee of Faculty of Medicine, Sohag University. There are adequate provisions to maintain privacy of participants and confidentiality of the data are as follows:

- The patients were given the option of not participating in the study if they did not want to.
- We put code number to each participant with the name and address kept in a special file.
- We hide the patients name when we use the research.
- We used the results of the study only in a scientific manner and not to use it in any other aims.

## **Statistical Analysis**

Statistical analysis was done by SPSS v26 (IBM Inc., Chicago, IL, USA). Quantitative parametric data were presented as mean and standard deviation (SD). Qualitative variables were presented as frequency and percentage (%).
